## 9.2 Plasma concentrations of concomitant AEDs

Blood samples for measurement of concomitant AED concentrations are collected at Visits 1, 2, 6, and 7. The concomitant AED concentrations will be summarized by visit and treatment group using the same descriptive statistics above (<LOQ values will be excluded) for the AED-PK-PPS. Only AED PK samples taken up to the (date of the last dose of study medication +1) will be included in the summary.

The AEDs investigated with mixed models will be those with data available for at least 10 evaluable subjects in one of the treatment groups (subset of AED-PK-PPS). An evaluable subject is defined as a subject:

- with at least one AED measure (>LOQ) at baseline and at least one AED assessment (>LOQ) during the maintenance period
- who received constant dose of AED for at least 14 days prior to the AED samples

Plasma concentration data for concomitantly administered AEDs (values <LOQ will be excluded) will be assessed by evaluating ratios of steady state levels during the Maintenance Period vs baseline levels. The baseline concentration is defined as the arithmetic mean concentration (if multiple concentrations are available at Visits 1 and 2) or the single concentration (if only 1 concentration is available at Visit 1 or Visit 2). Difference between log-transformed AED concentration at Visits 6 and 7 and baseline will be assessed using Mixed Model Repeated Measures (MMRM). The model will include log-transformed baseline concentration, visit, treatment, and treatment-by-visit interaction as fixed effects. An unstructured covariance structure will be used. If the model does not converge, an appropriate covariance structure will be used instead. Geometric least-squares (LS) means ratios and associated 90% CIs for each visit, by treatment group and PSL total will be calculated by exponentiation of the log-transformed data. Changes in AED concentration during the Maintenance Period and baseline will be considered clinically relevant if the respective 90% CIs fall entirely outside the conventional 0.80-1.25 limits. Forest plots will be provided on these (LS) means ratios and associated 90% CIs.

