- ^j The echocardiogram will be conducted at Visit 1. Echocardiograms will be repeated at Visit 6 for subjects continuing the OLE study. Subjects discontinuing will have an echocardiogram 30 days after last IMP intake at the SFU Visit (except if performed at Visit 6). A repeat echocardiogram will be performed for subjects with a new finding, Grade 2 (moderate severity), or Grade 3 (severe severity).
- ^k An echocardiogram will also be performed 6 months after last IMP intake for subjects exposed to >3 weeks to IMP and discontinuing the study (but not for subjects with <3 weeks exposure).
- ^l AED samples will ideally be taken immediately prior to dose of concomitant medication on each occasion. If this is not possible, then the sample may be taken at any time after dose and the timing of sample in relation to dose should be kept the same (± 1 hour) on each occasion for each subject. Therefore, the timing of visits for each subject when AED samples are collected should be scheduled approximately at the same time whenever possible. Assay of parent PSL and metabolites may be included in the AED panel of tests at Visits 6 and 7.
- ^m On Visits 6 and 7, unless the concomitant AED sample is within ± 5 minutes of a scheduled MITRA sample for PSL assay, a separate, additional MITRA sample will be taken at same time as the concomitant AED blood sample.
- ⁿ Subjects are requested to provide blood samples for measurement of PSL and metabolites whenever possible. On Visits 3, 5, and 6, site personnel should obtain blood samples for measurement of random PSL levels at any time between IMP intake and record accurately the time of last IMP intake and the time of sample collection. On Visits 4 and 7, blood samples for measurement of sparse PK profiles will be collected as follows: immediately before IMP intake (maximum 15 minutes before intake) and then 3 times after (between 30 minutes and 3 hours after IMP intake), taken at least 30 minutes apart. All samples may be taken either at home or in the site or partly at home and partly at the site.
- ^o For all female subjects, serum pregnancy test at Visits 1 and 7 (in case the subject enters into the OLE study) and where applicable. Urine pregnancy test will be used at other visits for female subjects of childbearing potential.
- ^p Seizure counts are collected on the subject's daily record card on a daily basis.
- ^q At each visit following an IMP dispensation, IMP should be presented to check for compliance.

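### SAP 9.2 logs an arithmetic-mean AED baseline, so for subjects with two baseline samples the expected within-arm ratio under no interaction is slightly below 1

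*SAP*

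**What the plan says.** SAP 9.2 sets the sampling schedule: "Blood samples for measurement of concomitant AED concentrations are collected at Visits 1, 2, 6, and 7". It then defines the baseline: "The baseline concentration is defined as the arithmetic mean concentration (if multiple concentrations are available at Visits 1 and 2"). A subject with just one of the two samples keeps that value unaveraged.

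The response is a log difference: "Difference between log-transformed AED concentration at Visits 6 and 7 and baseline will be assessed using Mixed Model Repeated Measures (MMRM"). The terms are listed as follows: "The model will include log-transformed baseline concentration, visit, treatment, and treatment-by-visit interaction as fixed effects". The output is on the ratio scale: "Geometric least-squares (LS) means ratios and associated 90% CIs for each visit, by treatment group and PSL total will be calculated by exponentiation". A change counts as clinically relevant when the whole 90% interval lies beyond 0.80 or 1.25. That rule is stated for the change between Maintenance and baseline, not for a comparison with placebo.

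Elsewhere the plan uses the log scale consistently. SAP 9.1 defines a geometric mean as the exponential of the average log concentration. Protocol 13.4.2 asks for the on-treatment to pre-treatment ratio and gives no averaging rule, so the arithmetic mean comes from the SAP alone.

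**The concern.** Each follow-up value is a single logged concentration. The baseline, where two samples exist, is averaged first and logged second. The two sides of the ratio are therefore on different footings, and the baseline side is higher on average. A subject with one baseline sample has no such shift, so its size also depends on how complete the baseline sampling was.

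At stake is the reading of each arm's ratio against fixed limits. A systematic downward shift looks like a small fall in AED level and hides part of a true rise. More subjects do not shrink it. The efficacy analyses and their type I error control are not involved; concomitant AED levels are one of the pharmacokinetic objectives listed under other objectives.

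**Working it through.** **Inputs.** Baseline rule, response, model terms, reported ratio and limits are from SAP 9.2. The within-subject CV, the between-subject log SD (0.6), the number per arm and independent normal errors on the log scale are assumptions. The documents state no sample size, power or expected ratio for this analysis, so there is no plan figure to reproduce.

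**Size of the shift.** Write log C = m + e for each sample, with e having SD s and s² = ln(1 + CV²). Then

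log[(C1 + C2)/2] = m + (e1 + e2)/2 + log cosh[(e1 - e2)/2].

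The last term is never negative. Since (e1 - e2)/2 has variance s²/2 and log cosh x is about x²/2, its expectation is about s²/4. With no interaction the expected log ratio is minus this amount. Exact values by numerical integration:

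| CV (assumed) | s² | s²/4 | exact shift | ratio, all with two samples | ratio, half with two |
|---|---|---|---|---|---|
| 10% | 0.0100 | 0.0025 | 0.0025 | 0.998 | 0.999 |
| 20% | 0.0392 | 0.0098 | 0.0097 | 0.990 | 0.995 |
| 30% | 0.0862 | 0.0215 | 0.0211 | 0.979 | 0.990 |
| 50% | 0.2231 | 0.0558 | 0.0531 | 0.948 | 0.974 |

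If e1 and e2 have correlation r beyond the subject mean, the shift falls to about s²(1 - r)/4.

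**Does the log-baseline covariate remove it?** No. The covariate changes the slope on baseline, not the average level of the change at the mean baseline. A simulated single-visit version of the model (five arms, 10 or 40 per arm) gave mean ratios of 0.990, 0.980 and 0.944 to 0.947 at CV 20%, 30% and 50%. With a geometric-mean baseline they were 0.9997 to 1.0009.

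**Relative to placebo.** With no interaction and the arithmetic baseline, the PSL ratio divided by the placebo ratio was 0.997 to 1.001.

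**Effect on the 0.80-1.25 rule.** With no interaction the rule was met most often at CV 50% and 10 per arm: 0.5% of simulations with the arithmetic baseline and 0.4% with the geometric one. An expected ratio of 0.80 from the shift alone would need a CV of about 139%. Near the limits (CV 30%, 40 per arm, 3,000 simulations):

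| True ratio | Flagged, arithmetic baseline | Flagged, geometric baseline |
|---|---|---|
| 0.75 | 43% | 32% |
| 0.80 | 9.3% | 4.9% |
| 1.25 | 2.1% | 5.7% |
| 1.30 | 10% | 18% |

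At exactly 0.80 or 1.25 a 90% interval should flag about 5%. The geometric baseline does so, while the arithmetic one is too high below and too low above.

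**The case against.** The strongest case on the other side is that the effect is small and visible.

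- **Sampling is controlled.** It is tempting to take the words "the sample may be taken at any time after dose" in footnote l of Table 5-1 (Protocol 5.2) as a sign of large within-subject variation. Read whole, the footnote prefers a pre-dose sample and otherwise asks for the same time after dose, within 1 hour, on every occasion. AED doses must be stable for 8 weeks before screening, evaluable subjects need 14 days of constant dose, and samples with major deviations are excluded from the AED-PK-PPS. This stands, and it favours the lower CVs.
- **Placebo carries the same shift.** Ratios are given by treatment group, so a careful reader would see it in placebo. This stands for interpretation, but the stated relevance rule does not use placebo.
- **False flags are very rare.** This stands when there is no interaction. It does not answer the asymmetry near the limits, although those flag rates rest on an assumed CV and on 40 subjects per arm taking the same AED. The SAP requires only 10 evaluable subjects in one group.

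**Conclusion.** The baseline definition does not match the log-scale model, and it shifts the expected within-arm ratio below 1 for subjects with two baseline samples. The shift is about 0.2% at 10% CV, 1% at 20%, 2% at 30% and 5% at 50%. It is less if some subjects have one sample or if Visits 1 and 2 are correlated beyond the subject mean. The CV is an assumption throughout.

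A reader might infer that every arm's observed ratio will be below 1, or that the plan will declare interactions that do not exist. The documents support neither. The shift is in the expected value, a single estimate can exceed 1, and the requirement that the whole interval lie beyond a limit almost rules out a flag from this cause alone. What remains is a minor systematic error that matters only when a true ratio is already near 0.80 or 1.25.

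**What to change.** In SAP 9.2, define the baseline as the geometric mean of the Visit 1 and Visit 2 concentrations, that is, the exponential of the mean of their logs; keep the single value where only one exists. This uses the definition already in SAP 9.1 and puts baseline, model and reported ratio on one scale.

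The cost is one phrase in the SAP and one line of derivation code. No sampling or model term changes. SAP 9.2 already excludes values below the limit of quantification, so the logs are always defined. If the analysis has already been run, repeat it with this baseline and report both; also showing each PSL ratio relative to placebo would remove the shift from the comparison.

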4.3 Other variables

4.3.1 Pharmacokinetic variables

Blood concentrations of PSL and metabolites will be determined from samples obtained in the study during the Titration and Maintenance Periods in order to investigate the following variables:

- The exposure-response relationship for PSL and active metabolite
- The population PK profiles of PSL and active metabolite

Blood concentrations of PSL and active (██████████) metabolite will be used to derive PK-population parameters (using population-PK analysis). Subjects will be asked to provide these samples whenever possible.

Blood concentrations of concomitantly administered AEDs will also be evaluated for evidence of DDI with PSL at steady state.

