13.4.2 Pharmacokinetic analyses

Blood concentrations of PSL and metabolites will be determined from blood samples obtained in the study, during the Titration and Maintenance Periods in order to investigate the PK of PSL and metabolites.

The PK parameters calculated include, $AUC_{(0-\tau)}$, AUC , C_{max} , t_{max} , $t_{1/2}$, C_{trough} , and $C_{max ss}$.

The PK variables will be derived from population PK modeling.

The PK parameters of PSL and metabolites will be listed and summarized using the following descriptive statistics: number of observations, geometric mean, lower and upper 95% CI, geometric coefficient of variation, arithmetic mean, SD, median, and minimum and maximum values. Graphical outputs over time will be produced on the trough plasma PSL concentrations.

Plasma concentration data for concomitantly administered AEDs will be assessed by evaluating ratios of steady state levels while on maintenance PSL vs Baseline (pre-PSL) levels.

An exploratory comparison of PSL blood levels derived from the MITRA samples with conventional venous sampling may be made. An exploratory evaluation of PSL metabolites may be undertaken.

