## 2.5 Other variables

### 2.5.1 Pharmacokinetic variables

Blood concentrations of PSL and metabolites will be determined from samples obtained in the study during the Titration and Maintenance Periods in order to investigate the following variables:

- The population PK profiles of PSL and active metabolite
- The exposure-response relationship for PSL and active metabolite

Blood concentrations of PSL and active [REDACTED] will be used to derive PK-population parameters (using population-PK analysis). Subjects will be asked to provide these samples whenever possible.

Blood concentrations of concomitantly administered AEDs will also be evaluated for evidence of drug-drug interaction with PSL at steady state.

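### The concomitant-AED interaction rule in SAP 9.2 is applied to each arm's own maintenance/baseline ratio, with no PSL-versus-placebo contrast, so change common to all arms can mask or exaggerate an interaction

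*SAP*

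**What the plan says.** The purpose is stated in Protocol 4.3.1: "Blood concentrations of concomitantly administered AEDs will also be evaluated for evidence of DDI with PSL at steady state". SAP 2.5.1 repeats it.

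Both documents define the measure as a before/after ratio. Protocol 13.4.2 says the AED data "will be assessed by evaluating ratios of steady state levels while on maintenance PSL vs Baseline (pre-PSL) levels", and Protocol 10.1 describes the same comparison. SAP 9.2 says they "will be assessed by evaluating ratios of steady state levels during the Maintenance Period vs baseline levels".

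SAP 9.2 fits a repeated-measures model to the log change from baseline at Visits 6 and 7: "The model will include log-transformed baseline concentration, visit, treatment, and treatment-by-visit interaction as fixed effects". The output taken from it is: "Geometric least-squares (LS) means ratios and associated 90% CIs for each visit, by treatment group and PSL total will be calculated by exponentiation". Forest plots show these same ratios. A change is called clinically relevant if the 90% CI lies entirely outside 0.80 to 1.25.

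Baseline is the arithmetic mean of the Visit 1 and Visit 2 concentrations when both exist. An AED is modelled if any one treatment group has at least 10 evaluable subjects. An evaluable subject has a value above the limit of quantification (LOQ) at baseline and in maintenance, and a constant AED dose for 14 days before sampling.

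SAP 9.3 leaves other PK analyses to a separate PK Data Analysis Plan, which was not available for this review.

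**The concern.** The samples being compared are 12 to 20 weeks apart (Week -4 and Day 1 against Weeks 12 and 16). AED levels can move over that time for reasons unrelated to PSL. Adherence may change under trial monitoring. Requiring values above LOQ at both times selects subjects. Taking the log of an arithmetic-mean baseline, against a single on-treatment sample, pulls every arm's ratio slightly below 1.

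To the extent that such change is shared by all arms, it cancels in a PSL/placebo ratio and stays in a within-arm ratio. The trial has a randomised concurrent placebo arm, and the model already contains the terms needed for the contrast. Where the SAP wants a placebo contrast it says so: SAP 8.1.2.1 asks for pairwise contrasts of each dose with placebo. SAP 9.2 has no equivalent. Taken literally, its rule could also flag the placebo arm, with no instruction for that case.

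At stake is whether a statement that PSL does or does not alter an AED's level is separated from time effects.

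**Working it through.** The plan gives no numerical figure to reproduce here; the question is what the rule tests.

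**Inputs from the documents.** Limits 0.80 and 1.25, symmetric on the log scale (ln 0.80 = -0.2231, ln 1.25 = +0.2231); 90% CI; threshold of 10 evaluable subjects in one arm.

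**Assumptions (not in the documents).** SD of the log maintenance/baseline ratio 0.2 to 0.4; 10 to 20 evaluable subjects per arm, equal in PSL and placebo; drift and true effect as shown.

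**Step 1: what is estimated.** Within-arm ratio = drift × true PSL ratio. For example, 0.85 × 1.5 = 1.275, and 0.90 × 0.80 = 0.72. In the PSL/placebo ratio a shared drift divides out.

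**Step 2: how often the rule fires.** 40,000 simulated trials per setting, one visit, normal log ratios, 90% t-interval. Ranges run over SD 0.2 to 0.4 and n = 10 to 20. The model in SAP 9.2 pools variance across arms, so its intervals would differ somewhat.

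| Shared drift | True PSL ratio | Within-arm rule (SAP 9.2) | Same rule on PSL/placebo |
|---|---|---|---|
| 0.90 | 1.00 | at most 0.6% | at most 0.5% |
| 0.70 | 1.00 | 25 to 89% | at most 0.5% |
| 0.90 | 1.50 | 14 to 50% | 25 to 88% |
| 0.85 | 1.50 | 7 to 11% | 25 to 88% |
| 0.90 | 0.80 | 19 to 73% | about 5% |
| 1.00 | 1.50 | 38 to 99% | 25 to 88% |

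**Step 3: the built-in baseline asymmetry.** Simulating one sample over the arithmetic mean of two, with no drug effect, gives a geometric mean ratio of 0.985 at a within-subject log SD of 0.25 and 0.962 at 0.40 (SDs assumed). This is small and common to all arms.

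**Step 4: cost in precision.** On the log scale the half-width grows by √(1/n₁ + 1/n₀) ÷ √(1/n₁), where n₁ is the PSL arm and n₀ placebo.
- Equal arms: √2 = 1.41.
- 10 PSL, 5 placebo: √(0.1 + 0.2) ÷ √0.1 = 1.73.
- 10 PSL, 3 placebo: √(0.1 + 0.333) ÷ √0.1 = 2.08.
- No placebo subjects on that AED: not estimable.

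With SD 0.25 and n = 20 per arm, the 90% half-width factor is exp(1.645 × 0.25 × √(1/20)) = 1.10 within an arm. It is exp(1.645 × 0.25 × √(2/20)) = 1.14 for one dose against placebo, and exp(1.645 × 0.25 × √(1/20 + 1/80)) = 1.11 for PSL total against placebo.

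**The case against.** A reader might infer that the placebo arm is discarded and the analysis is an uncontrolled before/after comparison. The documents do not support that. Placebo is a displayed treatment group (SAP 3.1), the AED analysis set is not limited to active arms (SAP 3.5.7.3), and ratios and forest plots are produced by treatment group. Placebo drift is visible beside each dose. What is missing is the formal contrast and a rule that uses it.

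A reader might also infer that ordinary drift would be declared an interaction. The rule needs the whole interval outside the limits. With a half-width factor of 1.10, drift of 0.90 alone gives about 0.82 to 0.99, and drift of 1.10 gives about 1.00 to 1.21; both lie inside. Drift alone becomes a problem only when it is large, such as the 0.70 in the table, and nothing in the documents suggests that size.

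Drift is also limited by design. AED doses must be stable for 8 weeks before screening and through the Treatment Period (Protocol 5.1). Footnote l of Protocol Table 5-1 allows non-trough sampling ("If this is not possible, then the sample may be taken at any time after dose"), but it also asks for the same timing relative to dose, within 1 hour, on each occasion. Sampling time is therefore a weak source of drift.

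Cancellation is only approximate. Being above LOQ on treatment, and still in the study at Visit 6 or 7, are post-randomisation conditions that may differ by arm.

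Finally, this is one of the PK objectives, not a primary or secondary one; an earlier drug-interaction study is listed (UP0013, Protocol 2.3); and the PK Data Analysis Plan may contain a placebo contrast.

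All of this stands and lowers the weight of the point. None of it supplies the contrast.

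**Conclusion.** The point holds in limited form. SAP 9.2 judges interaction on arm-level ratios, and its relevance rule ignores the placebo result; no PSL/placebo contrast appears there or in Protocol 10.1 and 13.4.2. The consequence is that shared change can mask or exaggerate a real interaction. Under the assumed values, drift of 0.85 cuts detection of a true 1.5-fold effect to 7 to 11%, against 25 to 88% with the contrast. Drift of 0.90 takes an effect exactly at the 0.80 limit from about 5% flagged to 19 to 73%. Drift of about 10% with no interaction would rarely be flagged.

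The sizes rest on drift, SD and subject numbers that the documents do not give. The finding that no contrast is specified rests on the text, subject to the PK Data Analysis Plan that was not seen. This is a cheap improvement, not a defect that invalidates the analysis.

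**What to change.** In SAP 9.2, from the same repeated-measures model:

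- Add the PSL-minus-placebo contrast for each dose and for PSL total at Visits 6 and 7, exponentiated, with its 90% CI.
- Apply the 0.80 to 1.25 relevance rule and the forest plots to these contrasts for AEDs that meet a pre-set minimum number of evaluable placebo subjects, for example 10, matching the existing criterion. The present threshold can be met by any single arm, so it does not secure a usable placebo group.
- Keep the within-arm ratios as descriptive output, and as the only output where placebo numbers are too small.

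No new data or model is needed. The cost is a wider interval: about √2 on the log scale for one dose with equal arms, and more when placebo is smaller. Some power is lost when there is no drift (38 to 99% falls to 25 to 88% for a true 1.5-fold effect under the assumptions above). If the PK Data Analysis Plan already contains the contrast, a cross-reference and alignment of the relevance rule would be enough.

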## 9.3 Other PK analyses/variables

Other PK analyses, including population PK analyses and exploratory PK analyses will be described in a separate PK Data Analysis Plan and will be reported separately.

## 10 SAFETY ANALYSES

The SS will be used to summarize and analyze all safety variables. In case of dosing administration error, summaries and analyses using the SS will be conducted according to actual treatment administered according to the rule described in Section 3.6. Safety data will be summarized for each treatment group and the PSL total group.

## 10.1 Extent of exposure

Extent of exposure will be based on the SS. The date of first dose is reported on First Administration of Study Medication CRF. The date of last dose is reported on the Study Termination CRF. If the date of last dose is missing due to lost to follow-up, the date of the last scheduled or unscheduled visit will be used.

The duration of study drug exposure for the Treatment Period will be calculated as the date of the last dose of study drug during the 16-week Treatment Period minus the date of first dose of study drug plus 1 day. Date of the last dose of study drug during the 16-week Treatment Period is defined as the overall study last dose date or the end date of the 16-week Treatment Period, whichever is earlier.

Exposure (in days) will be summarized as a continuous variable for the 16-week treatment period. The number and percentage of subjects with the following categories of durations of exposure for the Treatment Period will also be summarized: >0 weeks, >=4 weeks, >=8 weeks, >=12 weeks, >=16 weeks. The same summaries will be repeated for the subjects who received dose reduction during the Stabilization Period.

